12 STATISTICAL DESIGN AND ANALYSIS

12.1 Statistical Overview

The primary endpoint, defined as the proportion of participants experiencing one or more device- or procedure-related serious adverse events, will be evaluated at week 12. Secondary endpoints will be assessed at times specified in Section 3, including presentation of change from baseline by visits for glycemic parameters, liver enzymes and other cardiometabolic metrices.

12.2 Sample Size Considerations

The study plans to enroll 20 participants and test two treatment parameters (600 volts and 750 volts), with 10 participants treated in each group. As this study is intended to characterize device safety and feasibility outcomes, formal sample size and power calculations based on hypothesis testing against *a priori* statistical objectives are not relevant; a sample size of 10 in each group and 20 in total is considered to be sufficient for the objectives of this investigation.

12.3 Analysis Populations

The following analysis populations are defined for the study: Intent-to-Treat (ITT), modified Intent-to-Treat (mITT), Per-Protocol (PP) and Completed Cases (CC). The primary safety analysis will be performed on the ITT population. The primary effectiveness analysis will be performed on mITT population.

- Intent-to-Treat: The Intent-to-Treat population includes all enrolled participants as defined in Section 5.3 regardless of whether or not the participant received the full treatment.
- Modified Intent-to-Treat: The mITT population consists of the ITT population participants who received the target treatment (at least 6 cm of duodenum treatment) and that have at least one post-treatment follow-up.
- Per-Protocol: The Per-Protocol population is a subset of the mITT population and includes all participants who received the target treatment (at least 6 cm of duodenum treatment), have at least one post-treatment follow-up, do not have any major eligibility violations, and maintained stable glucose-lowering medications for 24 weeks post procedure.

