6.2.2.1 Peri-procedure

The dose of sulfonylureas or meglitinides will be reduced by 50% (or discontinued if on the lowest recommended dose) one day before the index procedure to avoid potential hypoglycemic risks. If an episode of documented or symptomatic hypoglycemia is experienced during the peri-procedure or transitional diet period, further reduction of sulfonylurea or meglitinide dose by 50% or discontinuation if on the lowest dose should occur.

Metformin should be held the day prior to endoscopy and resumed post procedure when the patient tolerates oral intake.

SGLT2i should be held three (3) days prior to the index procedure and resumed when the patient transitions to normal diet (after the 2-week transitional diet period).

GLP-1 Receptor agonists and DDP-4 inhibitors should be held in the peri-procedure period if the subject experiences significant nausea and/or vomiting and can be resumed once symptoms resolve at the discretion of the principal investigator.

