6.2.3 Guidelines for Managing Hyperglycemia

After the background medications have been titrated back to baseline level following the transitional diet period, participants with severe, persistent hyperglycemia should be offered treatment intensification.

In the event of suspected persistent hyperglycemia in a subject based on either symptoms of hyperglycemia (eg, thirst, polyuria, blurred vision), CGM readings of >250 mg/dL for > 30% of the time, or repeated fasting CGM readings above 270 mg/dL (e.g. occurring 3 days in a week), the investigator should perform additional laboratory tests to assess whether rescue therapy is warranted.

Participants meeting the following criteria should be offered rescue medication (i.e. intensification of glucose-lowering background medication and/or initiation of basal insulin).

- FPG > 270 mg/dL, confirmed by repeated measures more than 3 days apart, and no intercurrent cause can be identified, or
- HbA1c is >8.0% AND the interval improvement is <0.5% from baseline, by Week 12

After Week 24, participants should be offered treatment intensification if they do not reach their HbA1c target, which for most individuals is 7.0%.

The above criteria and medications are provided as a guideline. Investigators should always exercise his/her clinical judgement based on individual conditions to protect participant's safety and wellbeing.

Participants who meet rescue criteria before Week 24 should first complete the Week 24 visit activities within 5 days before initiation of the rescue medication to ensure that important trial endpoint measurements are collected and be provided the rescue therapy.

Medication changes and reasons for the changes will be documented on the eCRFs. Medications used to manage hyperglycemia are non-investigational and will not be provided by the sponsor.

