### 6. ANALYSIS POPULATIONS

Patients will be considered enrolled in the study once the patient has passed endoscopic screening. Screen failures are defined as patient who consented to participate in the clinical study and started the screening tests specified by the protocol but are not subsequently enrolled in the study.

The primary and secondary safety analyses will be performed using the ITT. The primary effectiveness analyses will be performed using the FAS population. The Per-Protocol population and Completed-Cases population will be used for the sensitivity analyses of the primary and secondary effectiveness endpoints.

*Intent-to-Treat*: The Intent-to-Treat population includes all enrolled patients, regardless of the patient having received the target treatment (at least 6cm of duodenum treated). The point of enrollment occurs when a patient has provided written informed consent and an energy delivery has been attempted during the index procedure.

*Full Analysis Set*: The FAS population consists of the ITT population patients who received the target treatment (at least 6 cm of duodenum treatment) and that have at least one post-treatment follow-up examination.

**Per-Protocol**: The Per-Protocol population is a subset of the FAS population and includes all patients who received the target treatment, do not have any major eligibility violations, and maintained stable glucose-lowering medications for 24 weeks post-procedure. The definition of what constitutes a major eligibility violations will be established before the study database is locked.

**Completed Cases**: The Completed Cases population is a subset of the Per-Protocol population and includes all patients who received the target treatment, do not have any major eligibility violations, and maintained stable glucose-lowering medications for 24 weeks post-procedure, and completed the final Week 48 End of Study Visit.

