# 9.1. Analysis of the Primary Safety Endpoint

Each table number and population will clearly state; results will be presented using the Table 1a design. Results will be tabulated based on the number of patients experiencing one or more device-related or procedure-related serious adverse events at 12 weeks post-procedure.

The statement of the primary research question that will be addressed is as follows:

What percentage of the patients in the ITT population experienced one or more device-related or procedure-related serious adverse events within 12 weeks (84 days) of the index study procedure?

The statement of the secondary research question is specific below:

Is there a difference in the percentage of patients in the ITT population who experienced one or more device-related or procedure-related serious adverse events within 12 weeks (84 days) of the index study procedure based on the generation of the device, voltage, and single vs. double treatment?

The following model will be used to compare the groups identified within each Comparison Set. The dependent variable is the classification of each patient relative to experiencing a device-related or procedure-related serious adverse events at within 12 weeks (84 days) of the index study procedure [variable: DRPRSAE]. Contrast statements will be used to derive the estimates for each pair-wise comparison of a group.

Version 1.0 Confidential Page 32 of 42

```
PROC GLIMMIX DATA=COMP_SET_1;
    CLASS COMP_SET_1_GROUP;
    MODEL DRPRSAE = COMP_SET_1_GROUP / DIST=BINARY LINK=LOGIT SOLUTION;
    RANDOM INTERCEPT / SUBJECT=SUBJID_N;
    LSMEANS TRTAN / DIFF CL;
RUN;
```

Sensitivity analyses will be performed using the FAS and PP populations. Results will be presented in the analysis table 14.4.1 entitled Summary of the Device-Related or Procedure-Related Serious Adverse Events Within 12 weeks (84 days) of the index study procedure (ITT Population) and table 14.4.1.1 entitled Summary of the Device-Related or Procedure-Related Serious Adverse Events Within 12 weeks (84 days) of the index study procedure (FAS Population) and table 14.4.1.2 entitled Summary of the Device-Related or Procedure-Related Serious Adverse Events Within 12 weeks (84 days) of the index study procedure (PP Population). Listing 16.4.11 entitled Adverse Events provides supportive data for Tables 14.4.1, 14.4.1.1, and 14.4.1.2 will be sorted by site number and patient number.

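### Both effectiveness sensitivity sets drop patients rescued for non-response before Week 24, so neither can test whether the FAS result is robust

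*Protocol*

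**What the plan says.** Protocol 12.3 restricts PP to mITT participants with no major eligibility violation who "maintained stable glucose-lowering medications for 24 weeks post procedure". SAP 6 repeats the condition; its FAS is the Protocol's mITT set. The Protocol names Completed Cases without defining it. The definition is in SAP 6: "The Completed Cases population is a subset of the Per-Protocol population", with the medication condition restated and Week 48 completion added.

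On the use of the sets, SAP 6 says: "The primary effectiveness analyses will be performed using the FAS population". For the checks on that analysis it says: "The Per-Protocol population and Completed-Cases population will be used for the sensitivity analyses of the primary and secondary effectiveness endpoints". No other effectiveness sensitivity analysis is given.

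Protocol 6.2.3 says rescue should be offered on either of two triggers. One is "FPG > 270 mg/dL, confirmed by repeated measures more than 3 days apart" with no intercurrent cause. The other is "HbA1c is >8.0% AND the interval improvement is <0.5% from baseline, by Week 12". Rescue means intensified background medication, basal insulin, or both. Participants who qualify before Week 24 should complete the Week 24 assessments before rescue starts.

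The plan handles data after rescue in two ways. Protocol 12.4.1 replaces them with the last pre-rescue value. SAP 7.3.1 analyses observed data and imputes only dates.

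For the primary safety endpoint, analysed on ITT, SAP 9.1 adds: "Sensitivity analyses will be performed using the FAS and PP populations".

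**The concern.** A patient rescued on the HbA1c trigger before Week 24 has changed medication and cannot be in PP or Completed Cases. The trigger uses a 0.5-point improvement, the same threshold as the Week 24 responder endpoint. Membership of both sets therefore depends on an earlier reading of the outcome being estimated.

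A sensitivity analysis is meant to test the main result under a different reasonable choice. Here both alternatives remove patients because they did poorly, and they share the same filter, so their agreement with each other adds nothing. A procedure with no effect could still show a mean improvement in PP. In a 20-patient feasibility study that may guide later development, agreement between PP and FAS could be read as support it does not give.

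The safety tables have a related weakness. FAS omits patients with under 6 cm treated, so an event that ends the procedure early is missing from it. PP also omits patients whose medication changed.

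**Working it through.** The plan gives no figure for this point (Protocol 12.2 declines a power calculation), so there is nothing to reproduce. The selection follows from the definitions; the simulation only shows its possible size.

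**Inputs from the documents.** Eligible HbA1c 7.5 to 10.0% (Protocol 5.1); the HbA1c rescue trigger (6.2.3); responder threshold 0.5 (Protocol 3); 20 patients. Baseline mean 8.6 and one scenario for mean change, -0.9, come from the second hydrothermal study described in Protocol 1.2.

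**Assumptions not in the documents.** Baseline SD 0.7, truncated to the eligible range; SD of change 0.9; Week 12 to Week 24 correlation 0.5 to 0.85; equal mean change at both weeks; true mean changes of 0 and -0.5; rescue uptake 100% or 50%. The FPG trigger is not modelled.

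**Rule.** Rescued if Week 12 HbA1c > 8.0 and improvement < 0.5; PP = not rescued.

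**Full uptake.** Ranges run from correlation 0.5 to 0.85.

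| True mean change | PP mean change | Responders, all patients without rescue | Responders, PP |
|---|---|---|---|
| 0 | -0.45 to -0.76 | 29% | 47 to 64% |
| -0.5 | -0.80 to -1.01 | 50% | 64 to 76% |
| -0.9 | -1.10 to -1.24 | | |

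With no true effect, about 64% meet the trigger, or 0.64 × 20 ≈ 13 patients.

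**Half uptake, true change 0.** This follows by arithmetic. Let q = 0.64 be the share meeting the trigger and m the full-uptake PP mean. The overall mean is 0, so the triggered patients average -(1 - q)m/q. With uptake u, PP mean = -uq × (triggered mean)/(1 - uq).
- m = -0.45: triggered mean = 0.36 × 0.45/0.64 = 0.25; PP mean = -0.32 × 0.25/0.68 = -0.12.
- m = -0.76: triggered mean = 0.36 × 0.76/0.64 = 0.43; PP mean = -0.32 × 0.43/0.68 = -0.20.

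The same weighting for responders gives 34 to 38%, against 29% overall.

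**Other spreads.** With SD of change 0.8 to 1.2, correlation 0.7 and half uptake, true changes of 0, -0.5 and -0.9 give PP means of -0.15 to -0.23, -0.63 to -0.71 and -1.00 to -1.07. The shift disappears if the Week 12 and Week 24 changes are uncorrelated.

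**Opposing exclusions.** Protocol 6.2.1 also permits changes for hypoglycemia, which may remove good responders. Suppose patients with Week 12 HbA1c below 7.0% (an assumed cut-off) also leave PP, with half rescue uptake, SD 1.0 and correlation 0.7:
- All of them leave: PP mean -0.47 against a true -0.50, and -0.77 against -0.90. The shift is cancelled or reversed.
- Half of them leave: -0.59 and -0.93. The shift is still toward benefit.

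**PP against FAS.** Full uptake, SD of change 0.9, true change 0, PP mean -0.45 to -0.76:
- Protocol rule (last pre-rescue value): FAS mean +0.05 to +0.16, so PP looks better.
- SAP rule (observed values) with an assumed rescue effect of -1.0: FAS mean = 0 - 0.64 × 1.0 = -0.64. PP looks worse at correlation 0.5, about equal at 0.7 and better at 0.85.

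With true change -0.5, SD 1.0, correlation 0.7 and the same rescue effect, observed FAS is -0.94 and PP -0.97. They agree, and both overstate the true change.

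**The case against.** A reader might infer that PP and Completed Cases can only flatter the procedure. The documents do not support that. Changes for hypoglycemia break the same condition and pull the other way, and under the SAP's observed-data rule PP can look less favourable than FAS.

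A reader might also infer that PP would be nearly empty, because planned holds and reductions around the procedure, such as "SGLT2i should be held three (3) days prior to the index procedure and resumed when the patient transitions to normal diet", break 24 weeks of stability if counted from the procedure. Protocol 6.2.1 returns patients to background medication after the transitional diet and asks for stability from then until Week 24, which is the more natural reading. What stands is that the PP wording does not say so.

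Full uptake is an upper case: Protocol 6.2.3 presents the criteria as guidance subject to clinical judgement. Stable background medication is also a protocol requirement, so asking for it in a per-protocol set is conventional.

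Consequences are limited as well. FAS, the primary effectiveness set, keeps rescued patients; Protocol 12.4.4 runs PP only where appropriate; the primary endpoint is safety on ITT; and SAP 7.1 calls the testing informative only.

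Finally, SAP 9 already counts failure for any reason as non-response at Week 24. That does not fully cover rescue: a patient whose observed Week 24 value has been improved by rescue medication would still count as a responder.

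These points limit direction and size. They do not restore PP or Completed Cases as a robustness check.

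**Conclusion.** The point holds. As written, the only two effectiveness sensitivity sets exclude patients rescued for non-response before Week 24, so neither can support the FAS result. This rests on the definitions alone.

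The size rests on assumptions. With no true effect, the apparent PP improvement is 0.45 to 0.76 points at full rescue uptake and 0.12 to 0.20 at half. Toward benefit is the expected direction relative to the change without rescue, provided the Week 12 and Week 24 changes are positively correlated and few good responders leave for dose reductions. How PP compares with FAS cannot be settled until the Protocol and SAP agree on post-rescue values. The issue affects interpretation of effectiveness, not a formal error rate, and should be corrected before analysis.

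**What to change.** 1. Define Completed Cases in SAP 6 as FAS patients who complete Week 48, without the medication condition.
2. Add a FAS sensitivity analysis that keeps every patient rescued before Week 24. Count them as non-responders, in the denominator, for both HbA1c responder endpoints; the SAP's 48-week endpoint now excludes patients who miss the Week 24 threshold. For continuous endpoints use the last pre-rescue value, which is the Protocol 12.4.1 rule that the SAP omits.
3. Keep PP if wanted, but label it as selected on response and not as evidence of robustness. Reconcile its 24-week stability condition with Protocol 6.2.1 and the planned changes in 6.2.2.1, so that it is clear whether those changes count as breaks.
4. State in SAP 9.1 that the FAS and PP safety tables are not robustness evidence for the ITT result.

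No new data are needed; rescued patients should already have pre-rescue assessments. The cost is SAP wording, a small amount of extra analysis, and sensitivity results that may look less favourable.

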12.4 Statistical Analysis

12.4.1 General Statistical Considerations

Analyses will be performed according to the general principles and directions outlined in these methods.

- Continuous data will be summarized using descriptive statistics: mean, standard deviation, median and range or interquartile range. Categorical variables will be summarized using frequency counts and percentages.
- For events which can occur multiple times in a single subject (e.g., adverse events), summaries
 will be comprised of the number and percentage of subjects with an event and the total number of
 such events. The proportion of subjects with events will be considered primary for analysis
 purposes.
- In general, available data will be used for all analyses, and missing data will not be replaced or
 otherwise imputed in summaries and analyses of study outcomes. However, to avoid biasing
 results due to confounding therapies, effectiveness data collected after an identified initiation of
 rescue medication for hyperglycemia will be replaced by the last value collected prior to such
 rescue intervention.
- Although the study is not explicitly powered to test *a priori* statistical objectives, comparisons citing p-values may be made between baseline metrics to values collected post-intervention, and between subgroups including the two treatment arms. In such cases, p-values will be presented using two-sided tests at a 0.05 level of significance or equivalently one-sided tests at a 0.025 level of significance.

12.4.2 Accountability and Demographics

The number of participants completing the study and withdrawing from the study will be presented along with reasons for withdrawal.

Descriptive summaries for baseline medical history and demographic characteristics including age, gender, height, weight, baseline BMI, diabetes history, glycemic parameters, and baseline medications will be presented.

12.4.3 Primary Endpoint Analysis

The primary endpoint of the study is the proportion of participants experiencing one or more device- or procedure-related serious adverse events within 12 weeks post-procedure. The analysis will be performed using the ITT population, then tabulated and reported for each treatment arm and overall. Fisher's exact test will be used to assess differences which may be present between groups

Additionally, an overall summary of AEs will be provided including the number of events and percent of participants with any AEs, SAEs, and UADEs. For each type of event, the number of events and number and percent of participants with the event will be provided. Separate summaries of all adverse events will be summarized by seriousness and by relationship to device and procedure.

Only events occurring at or after the index procedure will be counted for the purpose of safety analysis. Events occurring prior to the index procedure will be considered as medical history.

12.4.4 Effectiveness Analysis

Secondary endpoints are summarized in Section 3. The primary analysis of the study's secondary endpoints will be performed using the mITT population. The analysis will also be performed using the PP population when appropriate.

Results for these endpoints will be tabulated and reported for each treatment arm at each timepoint for which data were specified to be collected, using change scores from baseline where appropriate. For binary outcomes, Fisher's exact test will be used to assess differences which may be present between groups, while t-tests or Wilcoxon's rank-sum will be applied for continuous outcomes depending on the normality assumption. Effectiveness endpoints collected at multiple timepoints post-intervention (e.g., HbA1c) will also be assessed longitudinally using repeated-measures mixed-effects models with time as the repeated measure and treatment arm as a factor variable. Assessment of overall change from baseline and comparisons between treatment arms will then be predicated principally upon these repeated-measures analyses.

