### 4.2.1. Secondary Endpoints

**First Secondary Endpoint:** Procedure success: defined as successful treatment of at least 6 cm of duodenum segment.

**Second Secondary Endpoint:** Procedure time: defined as the time between the Endogenex catheter insertion and the catheter removal.

Third Secondary Endpoint: Change from baseline (post-baseline minus baseline) in HbA1c reported for each pre-specified study visit.

Note: The estimates will be derived using a mixed model repeated measure procedure; the 24 week result will be the principal time point of interest.

**Fourth Secondary Endpoint:** Change from baseline (post-baseline minus baseline) in Fasting plasma glucose (FPG) reported for each pre-specified study visit.

Note: The estimates will be derived using a mixed model repeated measure procedure; the 24 week result will be the principal time point of interest.

**Fifth Secondary Endpoint:** Change from baseline (post-baseline minus baseline) in Insulinresistance by HOMA-IR reported for each pre-specified study visit.

Note: The estimates will be derived using a mixed model repeated measure procedure; the 24 week result will be the principal time point of interest.

**Sixth Secondary Endpoint Part 6a:** Change from baseline (post-baseline minus baseline) in Post-prandial plasma glucose (PPG) based on mixed meal tolerance test (MMTT) reported for each prespecified study visit.

Note: The estimates will be derived using a mixed model repeated measure procedure; the 12 week result will be the principal time point of interest.

**Sixth Secondary Endpoint Part 6b:** Change from baseline (post-baseline minus baseline) in beta cell function based on mixed meal tolerance test (MMTT) reported for each pre-specified study visit.

Note: The estimates will be derived using a mixed model repeated measure procedure; the 12 week result will be the principal time point of interest.

**Sixth Secondary Endpoint Part 6c:** Change from baseline (post-baseline minus baseline) in the disposition index based on mixed meal tolerance test (MMTT) reported for each pre-specified study visit.

Note: The estimates will be derived using a mixed model repeated measure procedure; the 12 week result will be the principal time point of interest.

**Seventh Secondary Endpoint:** o Time in range, glucose variability by continuous glucose monitoring (CGM)

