## 7.2. Adjustments for Covariates and Stratification Factors

Data will be presented by individual subgroups if there are a sufficient number of patients to warrant the breakdown. There are no planned stratification factors to be included in the models of the 5 different Comparison Sets.

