### **Third Secondary Endpoint**

The distribution of this endpoint is continuous. The primary population for analysis of this endpoint will be the FAS population.

Change from baseline (post-baseline minus baseline) in HbA1c reported for each pre-specified study visit.

The pre-specified study visits where HbA1c is recorded is Week 4, 12, 24, 36, 48.

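### The stated terms of the principal repeated-measures models do not include the endpoint's own baseline value, so part of any baseline imbalance stays in the comparisons of small, non-randomised groups

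*Protocol*

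**What the plan says.** Protocol 12.4.4 describes the longitudinal analysis of effectiveness endpoints as "repeated-measures mixed-effects models with time as the repeated measure and treatment arm as a factor variable". It gives this model the leading role: "comparisons between treatment arms will then be predicated principally upon these repeated-measures analyses". Results are tabulated "using change scores from baseline where appropriate".

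SAP 4.2.1 repeats the approach for HbA1c, FPG, HOMA-IR and the meal-test endpoints: "The estimates will be derived using a mixed model repeated measure procedure". Week 24 is the principal time point for the first three and Week 12 for the meal-test endpoints. The outcome is a difference, for example "Change from baseline (post-baseline minus baseline) in HbA1c reported for each pre-specified study visit". The SAP lists no terms for this model. SAP 3 says the plan includes source code for the analysis of each endpoint, but the only code given is the logistic model for the primary safety endpoint (SAP 9.1), whose sole fixed effect is group.

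SAP 7.2 has covariate adjustment in its heading but names no covariate. Its one sentence on model content is "There are no planned stratification factors to be included in the models of the 5 different Comparison Sets". (SAP 7 defines two comparison sets, not five.)

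Protocol 12.2 plans 20 patients, "with 10 participants treated in each group", and Protocol 4.4 treats the 600V group before the 750V group. SAP 3 divides the 20 into 3 (600V single), 7 (600V double) and 10 (750V double). Comparison Set 1 compares these three groups; Comparison Set 2 is 3 vs 17.

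**The concern.** Change in a measure such as HbA1c usually depends on where the patient started. If groups differ at baseline, their mean changes will differ for that reason alone, whatever the regimen does. Nothing in this design balances baseline: allocation is sequential and one group has three patients. The baseline value is collected for every endpoint concerned, and the sponsor already treats baseline glycaemia as relevant. Baseline FPG is a planned subgroup factor in Protocol 12.4.5 and baseline HbA1c an optional one in SAP 7.3.2.

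At stake is how far the group differences on the secondary endpoints can be read as differences between regimens. Leaving the terms unstated also means that the choice of covariate could be made after the data are seen.

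**Working it through.** The documents give no SD, effect size or power for these endpoints, so there is no planned figure to reproduce.

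**Inputs**
- Group sizes 3, 7 and 10, and 3 vs 17 (SAP 3 and 7), all assumed to have data at the visit analysed.
- Baseline HbA1c SD 0.7 points: an assumption. A uniform spread over the 7.5 to 10.0% entry range (Protocol 5.1) gives 2.5/√12 = 0.72.
- Slope of change on baseline -0.2 to -0.6: an assumption. As a crude reference, the two earlier studies in Protocol 1.2 report falls of 1.2 points from a mean of 9.5% and 0.9 points from 8.6%, so -(1.2 - 0.9)/(9.5 - 8.6) = -0.33. That compares different studies and is not an estimate of the within-study slope.
- SD of change 0.9 points: an assumption.

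**Step 1. Size of a chance imbalance.** SE of the baseline mean difference = SD × √(1/n₁ + 1/n₂).
- 7 vs 10: 0.7 × √(1/7 + 1/10) = 0.345
- 3 vs 17: 0.7 × √(1/3 + 1/17) = 0.438

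**Step 2. What stays in the change-score contrast.** Remainder = |slope| × imbalance, for a 1-SE imbalance.

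| Slope | 7 vs 10 | 3 vs 17 |
|---|---|---|
| -0.2 | 0.07 | 0.09 |
| -0.4 | 0.14 | 0.18 |
| -0.6 | 0.21 | 0.26 |

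For scale, the responder threshold in the plan is 0.5 points.

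**Step 3. Precision.** Residual SD after adjustment = √(0.9² - slope² × 0.7²). The slope must be estimated from 20 patients. With three groups there are 17 within-group degrees of freedom, and the expected variance inflation is 1 + 1/(17 - 2), an SE factor of √(1 + 1/15) = 1.033.

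| Slope | Residual SD | Ratio to 0.9 | Net SE ratio (× 1.033) |
|---|---|---|---|
| -0.2 | 0.889 | 0.988 | 1.02 |
| -0.4 | 0.855 | 0.950 | 0.98 |
| -0.6 | 0.796 | 0.884 | 0.91 |

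**Step 4. Cross-check under different assumptions.** A simulation at one post-baseline visit (10 vs 10, equal baseline and follow-up SDs, 20,000 trials per setting) compared 95% confidence interval half-widths with and without adjustment. Adjusted intervals were 17%, 11%, 5% and 2% narrower at baseline-to-follow-up correlations of 0.3, 0.5, 0.7 and 0.8, and 1% wider at 0.9. Contrasts against the group of 3 behaved almost identically. The gain also disappears if follow-up is more variable than baseline, so that the slope of follow-up on baseline is near 1. At correlation 0.5 the adjusted half-width is still about 0.8 SD for 10 vs 10 and 1.2 to 1.3 SD against the group of 3.

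**The case against.** Four arguments on the other side have weight.

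*The documents are silent; they do not exclude baseline.* A reader might infer that the SAP rules out baseline adjustment. It does not: the sentence in SAP 7.2 concerns stratification factors, and Protocol 12.4.4 is a short description that also omits an arm-by-time term and a covariance structure. This stands, and the point is limited to baseline not being among the stated terms.

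*Change scores already deal with baseline.* A reader might infer that the whole baseline difference contaminates the contrast. It does not, because post minus baseline subtracts it. Only the part that depends on the starting value remains, as in Step 2. The SAP's Level 3 tables would also show baseline by group beside the change. That makes an imbalance visible, but the model estimate still does not account for it.

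*The precision gain is doubtful.* A reader might take the 1 to 12% fall in residual SD as the gain. That leaves out the cost of estimating the slope. On the same assumptions the net effect runs from a slight loss to about 9%.

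*Adjustment does not make non-randomised groups comparable.* In such groups the change-score and baseline-adjusted contrasts can answer different questions, and neither is automatically less biased. Calendar time, device generation and voltage move together between the 600V and 750V groups, and no baseline term separates them. This stands, and it is why both analyses should be shown.

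**Conclusion.** The point holds in a limited form. The models that carry the main effectiveness conclusions are described with time and arm only, and no passage in either document adds the endpoint's baseline value. With a baseline SD of 0.7 and a slope of -0.2 to -0.6, a 1-SE chance imbalance leaves about 0.07 to 0.21 HbA1c points in 7 vs 10 and 0.09 to 0.26 in 3 vs 17. At the upper end of 3 vs 17 that is about half the 0.5-point responder threshold. The calculation treats imbalance as if it arose by chance; with sequential groups the real difference could be smaller or larger.

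The reason to adjust is the imbalance, not precision.

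Severity is modest. The primary endpoint is safety and does not use this model. SAP 7.1 describes the testing as strictly informative, no power is claimed, and the comparisons remain very imprecise with or without adjustment.

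**What to change.** State the repeated-measures model in the SAP with these terms: visit, group, group-by-visit, and the endpoint's own baseline value, centred, as a single main effect. Report group means at the overall baseline mean. Show the unadjusted change beside them, because the groups are not randomised. Say in the text that adjustment covers measured baseline imbalance only, and not calendar time, device generation or voltage.

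Leave out baseline-by-visit or keep it as a sensitivity analysis. It adds one slope per visit: five for HbA1c (Weeks 4, 12, 24, 36, 48) and six for weight, which is also measured at Week 1. That is heavy for 20 patients.

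The cost is SAP wording and about one degree of freedom (17 to 16 for three groups at one visit), with a slight loss of precision if the slope is near zero. No new data are needed.
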